The safety analysis identified overall incidence and events of special interest: The safety analysis included all 34 infants. There were 23 adverse events in 15 participants and 5 serious adverse events (SAEs) in 5 participants, including 1 episode of hypotension, the only event related to sildenafil, in an infant receiving IV sildenafil (Table 2). This event was determined to be related to a faster than expected infusion rate of IV sildenafil. The event led to a data monitoring committee (DSMB) review of available data, and a review of all clinical sites' infusion methods and equipment. The protocol was changed prior to enrolling the remaining Cohort 2 subjects to include a

longer infusion time (30 minutes) and the dose was lowered by 50% to 0.125 mg/kg. When the study reopened, 2 additional subjects were enrolled without any related AEs.

Table 2 Summary of All Adverse Events in Phase 1 Study of Sildenafil

	Cohort 1 (N = 25)	Cohort 2 (N = 9)
Number of Events/Participants		
Number of AEs	13	10
Participants with at least one AE	8 (32.0%)	7 (77.8%)
Number of SAEs	1	4
Participants with at least one SAE	1 (4.0%)	4 (44.4%)
Severity (All AEs)		
Mild	7	3
Moderate	4	3
Severe	2	4
Highest Severity per Participant		
Mild	4 (16.0%)	2 (22.2%)
Moderate	3 (12.0%)	1 (11.1%)
Severe	1 (4.0%)	4 (44.4%)
Relationship (All AEs)		
Not related	13	9
Related	0	1
Strongest Relationship per Participant		
Not related	8 (32.0%)	6 (66.7%)
Related	0	1 (11.1%)

Abbreviations: AE, adverse event; N, number of participants; SAE, serious adverse event

Echocardiography is a reliable surrogate endpoint for the diagnosis of pulmonary hypertension in premature infants: With support from NHLBI (R34HL14038), members of the current study team (Drs. [name] and [name]) assigned 3 blinded pediatric cardiologists to review 483 echocardiograms from 49 infants < 29 weeks gestational age at birth (range 22–28) admitted to the neonatal intensive care units of UNC or Duke. PH diagnosis was a priori defined using tricuspid regurgitation jet and, if unavailable, a composite score of echocardiographic measures. The proposed score had high inter (modified Fleiss Kappa 0.759 (0.771, 0.801) and intra-rater reliability (Fleiss Kappa 0.847 (0.75, 0.931), and acceptable internal consistency (Cronbach's alpha 0.64)⁴⁶. Importantly, the score identified infants with PH with a prevalence (33%) and mortality (34%) comparable to prior reports. Mortality was significantly lower (10%) for infants not diagnosed with PH.

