4.2 Treatment Period

The treatment period will include Days 1-28 or last day of study drug if early withdrawal of study drug. The following information will be collected and recorded while the participant is on study drug:

1. Actual weight on study Days 7 (\pm 1 day), 14 (\pm 1 day), 21 (\pm 1 day), and 28 (\pm 1 day) of study drug administration
2. Date, time, amount, and route of study drug dose
3. All concomitant medications (including medications of special interest [Section 6.5.1])

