5.2 Participant Exclusion Criteria

An individual who meets any of the following criteria will be excluded from participation in this study:

1. Previous enrollment and dosing in this study, protocol number (NHLBI-2019-SIL), “Safety of Sildenafil in Premature Infants with Severe Bronchopulmonary Dysplasia (BPD)”
2. Previous exposure to sildenafil within 7 days prior to randomization*
3. Previous exposure to vasopressors within 24 hours prior to randomization*
4. Previous exposure to inhaled nitric oxide within 24 hours prior to randomization*
5. Previous exposure to milrinone within 24 hours prior to randomization*
6. Evidence of pulmonary hypertension or moderate/large patent ductus arteriosus (PDA) on the most recent echocardiogram performed within 14 days prior to randomization
7. Known major congenital heart defect requiring medical or surgical intervention in the neonatal period
8. Known allergy to sildenafil
9. Known sickle cell disease

10. Aspartate aminotransferase (AST) > 225 U/L < 72 hours prior to randomization
11. Alanine aminotransferase (ALT) > 150 U/L < 72 hours prior to randomization
12. Any condition that would make the participant, in the opinion of the investigator, unsuitable for the study.

**Participant will be reassessed prior to dosing to reconfirm eligibility criteria.*

Note: Exclusion from participation due to enrollment in other clinical trials, including IND trials, will be left to the judgement of the site principal investigator (PI). Investigator judgement should consider the safety of the participant.

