6 STUDY INTERVENTION

6.1 Study Product Description

In the US, sildenafil, in both IV and for oral suspension, has been approved for use in other populations and for other indications by the FDA¹.

Study dosing and escalation are described in Table 3. Refer to Section 6.1.3 for study drug packaging and labeling.

Table 3 Number of Participants (N) and Dosing Scheme

Cohort ¹	Treatment Group		Sildenafil Dosing ² (mg/kg q 8 hours)		Total (N)
	Placebo (N)	Sildenafil (N)	IV	Enteral	
1	10	30	0.5	1	40
2	10	30	1	2	40
3	10	30	2	4	40

Abbreviations: IV, intravenous; N, number of participants; q, every

1 Participants will be enrolled into cohorts sequentially (i.e., Cohort 1 then Cohort 2 then Cohort 3) based on safety.

2 Route of administration, IV or enteral, is left to investigator discretion.

Dose escalations for each sequential cohort will proceed as summarized in Table 4. DSMB safety review (Section 10) will be required prior to enrolling the next cohort.

Table 4 Dose Escalations for Each Sequential Cohort

	Study Days (Dose Numbers)							
	1-2 (1-6)	3-4 (7-12)	5-6 (13-18)	7-8 (19-24)	9-10 (25-30)	11-12 (31-36)	13-14 (37-42)	15 + (43 +)
Sildenafil Dose (mg/kg)								
Cohort 1								
IV	0.25	0.5	0.5	0.5	0.5	0.5	0.5	0.5
Enteral	0.5	1	1	1	1	1	1	1
Cohort 2								
IV	0.25	0.5	0.75	1	1	1	1	1
Enteral	0.5	1	1.5	2	2	2	2	2
Cohort 3								
IV	0.25	0.5	0.75	1	1.5	1.75	2	2
Enteral	0.5	1	1.5	2	3	3.5	4	4

Abbreviation: IV, intravenous

Dose escalation will occur if the infant is:

1. Receiving exogenous oxygen or respiratory support (nasal cannula or positive pressure from any device); and
2. AST < 225 U/L and ALT < 150 U/L at last check (within 14 days) prior and closest to dose increase.

An infant will meet respiratory criteria for dose escalation only if the infant is receiving exogenous oxygen or respiratory support (nasal cannula or positive pressure from any device) for at least 12 hours before the dose escalation. Infants who do not initially qualify for escalation should be reevaluated daily to ascertain whether they meet these criteria, and escalation must occur within 24 hours of an infant meeting all dose escalation criteria (respiratory and laboratory). If escalation does not occur within this timeframe, then a protocol deviation must be recorded.

Adjusting dose for weight

The actual weight should be reviewed weekly (plus or minus one day, Section 4.2) and the dose of the study drug may be adjusted.

Weaning Period Schedule

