Sildenafil is commonly used at higher doses to treat PH in infants. In clinical practice, it is recommended to wean from these higher doses to prevent rebound effects that may be seen with abrupt discontinuation of sildenafil. Although sildenafil used in this study is for prevention of PH, the target doses in Cohorts 2 and 3 are similar to those used for the treatment of PH.

For Cohorts 2 and 3, weaning of study sildenafil or placebo will begin following the last study dose on Day 28 or if the dose escalates to a dose of ≥ 0.5 mg/kg IV or ≥ 1 mg/kg enteral and the participant is withdrawn from the study. Wean by 25% of last study dose every 2 days until off. Participants should complete weaning after 6 days (Table 5).

Table 5 Weaning Schedule for Study Sildenafil or Placebo in Cohorts 2 and 3

Weaning Days	IV	Enteral
1-2	75% of last study dose	75% of last study dose
3-4	50% of last study dose	50% of last study dose
5-6	25% of last study dose	25% of last study dose
7	Discontinue	Discontinue

Abbreviation: IV, intravenous

If a participant in Cohort 2 or 3, escalates to a dose of ≥ 0.5 mg/kg IV (or ≥ 1 mg/kg enteral) and then is withdrawn from study drug, they will be withdrawn using the weaning schedule outlined above. Deviation from the weaning schedule for documented safety concerns will not result in a protocol deviation.

Weaning is not required for participants in Cohort 1 as the risk of rebound effects is likely minimal for infants receiving low-dose sildenafil.

6.1.1 *Study Placebos*

Intravenous placebo is sterile saline or dextrose 5% and enteral placebo is dextrose 5%.

6.1.2 *Acquisition*

Study drug and placebo will be acquired from the hospital pharmacy. Enteral sildenafil will be supplied to the site pharmacy by Pfizer, Inc. and will be labelled for investigational use. IV sildenafil will be supplied by the site using commercially available products (“off the shelf”).

6.1.3 *Formulation, Packaging, and Labeling*

Intravenous formulation: Only marketed IV formulation for IV administration will be used. This protocol will not specify the brand of product. Each product will be “off the shelf” as provided by the site’s pharmacy. Placebo will be an equal volume of sterile saline or dextrose 5%.

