12.2 Sample Size Considerations

The sample size of 30 (sildenafil) in each dose group is sufficient to estimate hypotension incidence with sufficient precision. Table 8 provides widths for 95% Wilson confidence intervals in the dose groups of size 30 and the total sildenafil treatment cohort of 90 with different incidence rates. If hypotension occurs with an incidence rate of 0.05, it has a 78% chance of being observed at least once in a dose group and a 99% chance of being observed at least once in the total sildenafil cohort.

Table 8 Widths for 95% Wilson Confidence Intervals

N = 30			N = 90		
Rate	Width	95% CI	Rate	Width	95% CI
0.1	0.22	0.04-0.26	0.1	0.13	0.05-0.18
0.2	0.28	0.10-0.37	0.2	0.16	0.13-0.29
0.3	0.31	0.17-0.48	0.3	0.19	0.22-0.40

Abbreviations: CI, confidence interval; N, number of participants

Populations for Analysis

Intention to Treat (ITT) Population: Participants whose parent or guardian signs informed consent and are randomized.

Per Protocol (PP) Population: Participants who receive at least 7 days of study medication within 9 days (to allow for one pause in medication administration for up to 48 hours).

Safety Population: Participants who receive at least 1 dose of study medication.

PK Population: All participants who have at least one interpretable PK sample.

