12.4 Final Analysis Plan

General Analysis Conventions

A comprehensive overview of planned statistical analyses will be provided in a separated statistical analysis plan.

Analysis results will be presented by placebo versus sildenafil, overall and by dose cohort. Data from participants assigned to placebo across cohorts will be pooled in result presentations.

Descriptive statistics such as number of observations, mean, median, standard deviation, minimum and maximum will be presented by treatment groups for continuous variables (such as age, weight, etc.). Other descriptive statistics such as counts, proportions, and/or percentages will be presented by group to summarize discrete variables (such as race, sex, etc.).

Participant Disposition and Study Drug Exposure

Study disposition, demographic and baseline characteristics, and study medication exposure will be summarized for the ITT Population. Study drug administration will be summarized by route (IV vs enteral), number of days of dosing, and reasons for final discontinuation of study drug.

Demographic and baseline characteristics

Demographic and baseline characteristics will include race, age, sex, and selected clinical variables recorded prior to initiation of study drug.

Safety

The primary safety endpoint is number and percent of hypotension events and will be summarized for the PP and Safety Population.

Serious adverse events will be presented overall and by each Medical Dictionary for Regulatory Activities (MedDRA) system organ class and preferred term. Severity and relationship to sildenafil or placebo will be provided.

Events of special interest will be presented overall and summarized by participant characteristics.

Prior and concomitant medications will be summarized by World Health Organization (WHO) drug class.

Laboratory data, including change from baseline, will be tabulated by treatment groups.

PK Analysis Plan

A comprehensive overview of planned PK analyses will be provided in a separated PK analysis plan.

Pharmacokinetic parameters will be estimated by population PK approach using nonlinear mixed effects modeling in NONMEM. The influence of covariates on PK parameters will be explored.

Biomarkers

We will relate the concentration of biomarkers (Section 8.2) to the development of and severity of PH in participants exposed to placebo.

Preliminary Effectiveness

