A multivariable mixed-effects model will be used to explore the relationship between the maximum and total dose of sildenafil and change in PH, death, and death or PH at 28 days of study drug and at the end of hospitalization or 52 weeks PMA, whichever comes first. We will use 52 weeks PMA because we found that 95% of infants with severe BPD died or were discharged home by this time.⁷

Planned sensitivity analyses of the primary endpoint

To address the potential effect of multiples enrolled in the study on the primary endpoint, we will conduct the following 2 sensitivity analyses:

- Sensitivity analysis #1 using only the first randomized sibling from any multiple gestations.
- Sensitivity analysis #2 using generalized estimating equations (GEE) with log link random effect for siblings to compute ratios of hypotension between the sildenafil and placebo groups.

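### If total dose means dose received, the preliminary-effectiveness model relates 28-day death to an exposure that death itself cuts short, which tends to make an inert drug look protective (minor)

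*Combined protocol and SAP*

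**What the plan says.** Under Preliminary Effectiveness, section 12.4 of the protocol proposes an exploratory multivariable mixed-effects model. Its exposures, outcomes and first time point are "the maximum and total dose of sildenafil and change in PH, death, and death or PH at 28 days of study drug". A second, later time point is whichever is earlier of 52 weeks PMA and the end of the hospital stay. The section does not say whether dose is assigned or received, whether weaning doses count, or which analysis population is used. It names no landmark and no time-varying exposure. The same section defers detail to a separate SAP, which was not among the documents available.

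The dosing window is set in section 4.2: "The treatment period will include Days 1-28 or last day of study drug if early withdrawal of study drug". The date, time, amount and route of each dose are recorded, so dose received can be computed. Section 6.1 gives the schedule: "Dose escalations for each sequential cohort will proceed as summarized in Table 4". For Cohorts 2 and 3 it adds a wean: "Wean by 25% of last study dose every 2 days until off".

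Section 12.4 also states that "Analysis results will be presented by placebo versus sildenafil, overall and by dose cohort". Preliminary effectiveness is a secondary objective, and the model itself is described as exploratory.

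**The concern.** Exposure and outcome share one window. If total dose is the amount actually given by Day 28, an infant who dies on Day 10 cannot have a high total, and a full-course survivor cannot have a low one for its cohort. Low dose is then partly a consequence of death. A model that treats end-of-treatment total as a fixed covariate attributes that consequence to the drug, and the artefact tends to favour more sildenafil.

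The stakes are modest. The model is exploratory, and the by-arm and by-cohort results will be reported beside it. Still, section 2.2 says that studies in this population should inform the design of a pivotal efficacy trial, and it reports higher mortality at the highest sildenafil dose in older children. A dose-death coefficient biased towards benefit would be an unhelpful guide on that question.

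**Working it through.** The plan gives no figure for this model, so there is none to reproduce first.

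**Inputs from the protocol.** Table 4 IV doses, three a day for 28 days (84 doses); enteral doses are twice these. There are 30 sildenafil and 10 placebo infants in each of three cohorts.

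**Inputs assumed.** 28-day mortality is not given, so 2%, 3%, 5% and 10% are used. Section 2.2 reports "Mortality was significantly lower (10%) for infants not diagnosed with PH", but in another cohort and with no 28-day limit. Because section 5.2 excludes "Evidence of pulmonary hypertension or moderate/large patent ductus arteriosus (PDA) on the most recent echocardiogram performed within 14 days prior to randomization", that 10% is taken as the top of the range. Early-stop rates are not given either; 0%, 20% and 40% are used.

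**Step 1: full-course IV totals (mg/kg).**
- Cohort 1: 6×0.25 + 78×0.5 = 40.5
- Cohort 2: 6×(0.25+0.5+0.75) + 66×1 = 75
- Cohort 3: 6×(0.25+0.5+0.75+1+1.5+1.75) + 48×2 = 130.5

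If weaning doses count, survivors add 6×(0.75+0.5+0.25) = 9 times the last dose. That is 9 and 18 mg/kg in Cohorts 2 and 3, which widens the gap.

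**Step 2: mean total for infants who die.** Let D(k) be the cumulative dose after k doses, with death equally likely after each of doses 1 to 84. The mean is ΣD(k)/84. For Cohort 1, the first 6 terms sum to 0.25×21 = 5.25. The other 78 sum to 78×1.5 + 0.5×(78×79/2) = 1,657.5. The mean is 1,662.75/84 = 19.8.

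| Cohort | Infants who die | Survivors | Ratio |
|---|---|---|---|
| 1 | 19.8 | 40.5 | 0.49 |
| 2 | 34.2 | 75 | 0.46 |
| 3 | 53.0 | 130.5 | 0.41 |

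If the dose in the interval of death is not given, the ratios are about 0.48, 0.44 and 0.39. The Per Protocol population ("Participants who receive at least 7 days of study medication within 9 days") does not remove the gap: among infants with at least 7 days of drug the ratios are 0.61, 0.58 and 0.52.

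**Step 3: inert-drug simulation.** Death is independent of arm and cohort, placebo dose is 0, all dosing is IV and weaning is not counted. Death by Day 28 is regressed on total dose received in all 120 infants. The table shows the percentage of trials with z < -1.96 (nominal 2.5%) at 2%, 3%, 5% and 10% mortality.

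| Early stops other than death | Test | 2% | 3% | 5% | 10% |
|---|---|---|---|---|---|
| None | Score | 9 | 19 | 40 | 75 |
| 20% of survivors | Score | 4 | 9 | 23 | 54 |
| 40% of survivors | Score | 2 | 3 | 11 | 30 |
| None | Firth Wald | 2 | 6 | 24 | 63 |
| 20%, at random | Firth Wald | 0.5 | 3 | 12 | 51 |
| 20%, all lower-risk infants | Firth Wald | 0.1 | 2 | 9 | 38 |
| 40%, all lower-risk infants | Firth Wald | 0 | 0.3 | 2 | 15 |

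With no other stops, the median Firth odds ratio per 40.5 mg/kg was 0.54, 0.52, 0.50 and 0.48. With stopping, it stayed below 1 in every setting (0.46-0.69). Replacing dose received with assigned dose gave score-test rates of 0.8-2.2%.

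**Step 4: reach.**
- Death or PH (PH assumed 20%): odds ratio 0.95, 0.93, 0.88, 0.80.
- In-hospital death (5% by Day 28 plus 5% later): score-test rate 20%, against 40% for 28-day death at 5%.
- Maximum dose, all infants: score-test rate 1-7%. It grows if cohort is in the model but stays below total dose. In sildenafil infants with 5% mortality and 20% stopping, by a penalised likelihood ratio test, the rates are 33% and 76%.
- PH alone: not assessed, and no claim is made.

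**The case against.** The strongest reply is that the premise is a reading, not a statement. Section 12.4 gives one sentence and leaves definitions to a separate SAP, which may define total dose, set a landmark or use assigned dose. That stands, and the point is conditional on it. But nothing in the available text removes the problem, and recording every dose makes dose received the natural reading.

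Second, the largest rates assume that nobody stops drug except by death. Sections 5.5.1 and 5.5.2 provide for parental withdrawal, suspension beyond 48 hours, raised ALT or AST, and unmasking. This stands too. Stopping shrinks the effect, and at 2-3% mortality Firth Wald rates are then near or below nominal. With so few deaths, sparse data are the larger problem.

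Third, the protocol has rules that push both ways. Under section 6.1, infants off oxygen and respiratory support do not escalate, so healthier infants may receive less drug, which may offset part of the bias. Under section 5.5.1, starting a vasopressor or inhaled nitric oxide ends study drug, which may add to it. One scenario held half of the lower-risk infants at a lower dose, with sicker infants at four times their risk of death. Total dose still looked protective: in sildenafil infants at 5% mortality with 20% stopping, 44% of trials by a penalised likelihood ratio test, against 56% without that feature. Low-risk infants stopping drug at discharge was not modelled as such.

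A reader might infer that the estimate must always favour more sildenafil. The documents do not support that: with no other stops the odds ratio was below 1 in 90% of simulated trials with a death at 2% mortality, and with stopping in 79-88%. A reader might also take the false-protective rates as the trial's error rates. They are not: no significance test is planned, and the planned mixed model is not specified closely enough to simulate.

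**Conclusion.** The point holds as a minor one. If total dose means dose received, the planned coefficient for death at 28 days is biased towards benefit, because death shortens the exposure. The median odds ratio was below 1 in every scenario tried. The size is uncertain, because it depends on mortality and stopping rates that the documents do not give, and on IV dosing and uniform death times. If assigned dose is meant, this bias does not arise. The problem is mainly total dose against 28-day death. It is weaker for death or PH, for later death and for maximum dose. It does not touch the primary safety endpoint or the by-arm and by-cohort summaries.

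**What to change.** In section 12.4, for death and for death or PH, do not enter end-of-treatment total dose received as a fixed exposure. Analyse dose received in one of two ways:
- with a landmark, for example dose through Day 14 among infants alive then, against later outcome; or
- as a time-varying exposure, using the dose dates and times already collected.

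Show assigned cohort dose beside it, noting that the cohorts are enrolled sequentially and are not randomised against each other, so differences between them may reflect calendar time. State whether total dose is assigned or received, the analysis population, and whether weaning doses count. If the separate SAP already does this, align the protocol sentence with it.

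The cost is wording only, with no new data. The main downside is that a landmark drops earlier deaths from an already small number.

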13 SOURCE DOCUMENTS AND ACCESS TO SOURCE DATA/DOCUMENTS

An eCRF will be used to record participation data. The eCRF will be used for the recording of all historical participant information and study data as specified by this protocol. The eCRF must be completed by designated and trained study personnel.

According to ICH E6 (R2), source data are defined as all information in original records and certified copies of original records of clinical findings, observations, or other activities in a clinical trial necessary for the reconstruction and evaluation of the trial. Source data are contained in source documents (original records or certified copies). Source documents are defined as original documents, data, and records (e.g., hospital records, clinical and office charts, laboratory notes, memoranda, participants' diaries or evaluation checklists, pharmacy dispensing records, recorded data from automated instruments, copies or transcriptions certified after verification as being accurate and complete, microfiches, photographic negatives, microfilm or magnetic media, x-rays, participant files, and records kept at the pharmacy, at the laboratories, and at medico-technical departments involved in the clinical trial).

It will be the responsibility of the investigators to ensure that the regulatory binder at the site is maintained. The study file will contain, but will not be limited to:

- Current package inserts, and all previous versions
- Current study protocol
- Protocol amendments (if applicable)
- Manual of Procedures
- Informed permission form (blank)
- IRB approved informed permission form
- Revised informed permission forms and/or all addenda (blank)
- IRB registration or other documentation of IRB compliance with applicable regulations
- Documentation of IRB/REB approval of protocol, permission form, any protocol amendments, and any permission form revisions
- Annual IRB/REB updates and approvals
- All correspondence between the investigator and IRB/REB

Each participating site will maintain appropriate medical and research records for this trial, in compliance with Section 4.9 of ICH E6 (R2), and regulatory and institutional requirements for the protection of confidentiality of participants. Each site will permit authorized representatives of the sponsor, its designees, and appropriate regulatory agencies to examine (and, when required by applicable law, to copy) clinical records for the purposes of quality assurance reviews, audits, and evaluation of the study safety and progress. These representatives will be permitted access to all source data.

